6.3. Other Endpoints

Not applicable

6.4. Covariates

As for the safety and effectiveness of Vfend, there are no covariates identified from clinical study data thus far obtained.

7. HANDLING OF MISSING DATA

When the seriousness/outcome of adverse events and action taken with Vfend for the adverse events are missing, these data are handled as “unknown” for counting. Because information on causal relationship will be collected by dosage form in this study, causal relationship will be handled as “missing” only when it is missing for all of injection, tablet, and dry syrup and will be handled as “related” for counting. If data on effectiveness endpoints are missing, they will be handled as “missing.”

The strategy for handling data with uncompleted cleaning is described below.

- Items of missing data: The items will be handled as missing (category of categorical variable is “unknown”) for both tabulation and listing.

- Items of inconsistent data: The items will be handled as missing for both tabulation and listing. However, the list of data handling will be separately prepared.
- No signature: Descriptions in the case report form without the signature of the contracted physician (including the case report form with the signature of an uncontracted physician only) will be handled as missing for both tabulation and listing.

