Children (Aged 2 to <12 and ≥12 whose body weight is less than 50 kg)	After the administration of Voriconazole injection, a recommended maintenance oral dose of voriconazole following injection therapy is 9 mg/kg/dose twice daily between meals. Dose may be increased by 1 mg/kg at a time if poorly responded, and dose in intolerant patients should be reduced by 1 mg/kg at a time (unless the dosage was at its maximum 350 mg, in which case, dose should be reduced by 50 mg at a time). A total daily dosage should not exceed 350 mg/dose twice daily.
Children (Aged ≥12 whose body weight is 50 kg or more)	After the administration of Voriconazole injection, a recommended maintenance oral dose of voriconazole following injection therapy is 200 mg/dose twice daily between meals; which may be increased up to 300 mg/dose twice daily if poorly responded.

<Dry Syrup>

Adult (body weight ≥40 kg)	A recommended oral dose of voriconazole is 300 mg/dose twice daily between meals on day 1, and 150 or 200 mg/dose twice daily between meals on day 2 and thereafter. Dose may be increased depending on condition of patients or if poorly responded; provided that a total daily dosage should not exceed 400 mg/dose twice daily on day 1 and 300 mg/dose twice daily on day 2 and thereafter.
Adult (body weight <40 kg)	A recommended oral dose of voriconazole is 150 mg/dose twice daily between meals on day 1, and 100 mg/dose twice daily between meals on day 2 and thereafter. Dose may be increased from day 2 onward depending on condition of patients or if poorly responded; provided that a total daily dosage should not exceed 150 mg/dose twice daily.
Children (Aged 2 to <12 and ≥12 whose body weight is less than 50 kg)	After the administration of Voriconazole injection, a recommended maintenance oral dose of voriconazole following injection therapy is 9 mg/kg/dose twice daily between meals. Dose may be increased by 1 mg/kg at a time if poorly responded, and dose in intolerant patients should be reduced by 1 mg/kg at a time (unless the dosage was at its maximum 350 mg, in which case, dose should be reduced by 50 mg at a time). A total daily dosage should not exceed 350 mg/dose twice daily.

Children (Aged ≥ 12 whose body weight is 50 kg or more)	After the administration of Voriconazole injection, a recommended maintenance oral dose of voriconazole following injection therapy is 200 mg/dose twice daily between meals; which may be increased up to 300 mg/dose twice daily if poorly responded.

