7.7. Data analysis

The details of analysis method on data collected in this study shall be described in the Statistical Analysis Plan to be separately prepared.

1) Definition of analysis set

The safety analysis set shall include patients for whom the registration in this study and administration of this product have been confirmed.

Two analysis sets, which are clinically-evaluable analysis set and mycological analysis set, shall be defined as the effectiveness analysis set. The clinically-evaluable analysis set includes patients for whom performance of clinical response was confirmed among patients in the safety analysis set. The mycological analysis set include

patients for whom microbiological response was assessed among patients in the clinically-evaluable analysis set.

2) Analysis method

(1) Safety analysis

The incidence of adverse reactions shall be calculated for each event. Also, the factors affecting the occurrence of adverse reactions shall be evaluated as necessary.

(2) Effectiveness analysis

The clinical response rate (the number of responders / the number of clinically-evaluable patients excluding indeterminate patients) and its 95% confidence interval shall be calculated for the clinically-evaluable analysis set. Also, the eradication rate (the number of patients with mycological eradication + presumed eradication / the number of patients for mycological analysis excluding indeterminate patients) and its 95% confidence interval shall be calculated for the mycological analysis set.

Detailed methodology for summary and statistical analyses of data collected in this study will be documented in a Statistical Analysis Plan of this study and maintained by Pfizer. The SAP may modify the plans outlined in the protocol; any major modifications of primary endpoint definitions or their analyses would be reflected in a protocol amendment.

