6. ENDPOINTS AND COVARIATES

6.1. Safety Endpoints

- Adverse drug reactions: Adverse events determined to be related to Vfend by the physician
- Adverse events: All-causality adverse events
- Serious adverse events or adverse drug reactions: Adverse events or adverse drug reactions determined to be serious by the physician.
- Important identified risks determined to be safety specifications are listed below.
 - Hepatic toxicity
 - QT prolongation, ventricular tachycardia, ventricular fibrillation, arrhythmia, complete atrioventricular block
 - Visual events
 - Phototoxicity
 - Peripheral neuropathy such as Guillain-Barre syndrome
 - Renal disorder
 - Hematologic disorder
 - Interstitial pneumonia
 - Cardiac failure
 - Consciousness disorder

Specific event terms to be handled as safety specifications will be specified separately.

- Events to be handled as major investigation items are listed below.
 - Hepatic toxicity
 - Visual events

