8.2.3.1. Adverse Drug Reactions

- **All adverse drug reactions**

The number and proportion of patients with adverse drug reactions will be tabulated by SOC and PT. Also by diagnostic name (name of infection), the number and proportion of patients with adverse drug reactions will be tabulated by SOC and PT.

- **Serious adverse drug reactions**

The number and proportion of patients with serious adverse drug reactions will be tabulated by SOC and PT. In addition, the number and proportion of patients by known/unknown serious adverse drug reactions will be tabulated by SOC and PT.

- **Details of adverse drug reactions**

The number and proportion of patients with adverse drug reactions will be tabulated by SOC and PT for each of the following items.

- Seriousness [serious, non-serious]
- Known/unknown [known, unknown]
- Intervention [discontinuation, temporarily discontinued, dose reduction]
- Outcome [not recovered, recovered with sequela, recovering, resolved/recovered, unknown]

In addition, the number and proportion of patients with adverse drug reactions meeting all of the following conditions will be tabulated by SOC and PT.

- Seriousness is “non-serious”
- Intervention is “discontinuation,” “temporarily discontinued,” or “dose reduction”
- Outcome is “not recovered” or “recovered with sequela”

If the same adverse event (the same PT) occurs more than once in the same patient, it will be handled as follows in the tabulation of the number of patients with events:

- Seriousness: If both serious and non-serious events are reported, “serious” will be adopted.
- Known/unknown: If both known and unknown events are reported, “unknown” will be adopted.
- Number of days to onset: The number of days to the first event will be adopted.
- Intervention: If multiple types of action taken with Vfend for the adverse events are reported, one of discontinuation, temporarily discontinued, dose reduction, or none, in descending order of precedence, will be adopted.
- Outcome: The outcome of the last occurring event will be used.

- **Safety specifications**

The number and proportion of patients with events will be tabulated. In addition, the number and proportion of patients with safety specifications by intervention and outcome will be tabulated by SOC and PT.

- **Major investigation items**

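### In children who changed dosage form, a 'not related' mark for the earlier form switches off the SAP's missing-means-related default, even when causality for the form in use at onset is blank.

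*SAP*

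**What the plan says.** SAP 7 (Handling of Missing Data) explains its rule by the way the data are collected: "Because information on causal relationship will be collected by dosage form in this study". Causality then counts as missing "only when it is missing for all of injection, tablet, and dry syrup and will be handled as" related.

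SAP 6.1 (Safety Endpoints) fixes what enters the reaction tables: "Adverse drug reactions: Adverse events determined to be related to Vfend by the physician".

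Protocol 7.2.1 prints the paediatric oral regimens, for tablets and for dry syrup, as a continuation of injection: "After the administration of Voriconazole injection, a recommended maintenance oral dose of voriconazole following injection therapy". Children with more than one form are therefore expected.

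Reaction counts are the planned safety output. Protocol 7.7 says "The incidence of adverse reactions shall be calculated for each event", and SAP 8.2.3.1 says "The number and proportion of patients with adverse drug reactions will be tabulated by SOC and PT".

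No section has a rule for a record that is blank for some forms and filled for others. None separates a form never received from one received but not assessed.

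**The concern.** The all-blank condition has a sensible purpose. A child treated only by injection will have nothing to enter for tablet or dry syrup, and those blanks should not turn a clear 'not related' into 'related'. But the condition does not ask which forms the child received, so in a child who switched it treats an unassessed form as if it had never been taken.

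Take a child on injection for Days 1 to 10 and tablets from Day 11, with an event on Day 30. Injection is marked 'not related' and tablet is blank. One filled field means causality is not missing under SAP 7. No form is marked related, so the event is not a reaction under SAP 6.1. Yet the form in use at onset was never judged.

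This runs against the plan's cautious handling elsewhere. Wholly missing causality goes to 'related', and for repeat events SAP 8.2.3.1 lets serious override non-serious and unknown override known.

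Reaction status feeds the tables by organ class and term, the reaction-based analyses of hepatic toxicity and visual events, time to onset, and the subgroup risk ratios (SAP 8.2.3.4) that are screened at 2 or above and 0.5 or below (SAP 8.2.3.5). The oral phase is where events would be lost, and it includes the dry syrup that Protocol section 5 describes as the new dosage form approved alongside the paediatric indication.

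**Working it through.** The SAP gives no figure for this point, so there is none to reproduce. The check has two parts.

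**1. What the rule does to each possible record**

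Each of the three forms can be related, not related or blank, which gives 3 × 3 × 3 = 27 patterns. Apply SAP 7 (all blank counts as related) and SAP 6.1 (otherwise a reaction only if some form is marked related):

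- At least one form related: 27 − (2 × 2 × 2) = 19 patterns, counted as reactions.
- All blank: 1 pattern, counted as a reaction.
- The remaining 7 patterns are not counted. One is 'not related' for all three forms; the other 6 contain at least one blank.

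Of those 6, three have one 'not related' and two blanks, and three have two 'not related' and one blank. The SAP cannot tell two cases apart here. 'Not related' for injection with two blanks is the normal record of a child on injection alone, and also that of a child who moved to tablets and had causality for tablets left out.

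| Injection | Tablet (in use at onset) | Dry syrup (never taken) | Counted as a reaction? |
|---|---|---|---|
| blank | blank | blank | yes |
| not related | blank | blank | no |
| not related | not related | blank | no |

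The second row is the problem. It carries no more information about the tablet than the first, yet it gets the opposite result.

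**2. Possible size**

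Inputs:

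- Planned number of patients: 100 (Protocol 7.5.1).
- Planning rates: hepatic toxicity 19.0%, visual events 42.9% (Protocol 7.5.2), so 19.0 and 42.9 expected cases per 100.
- Share of children who switch form, *s* = 60%: an assumption.
- Share of switchers' events with the pattern, *m* = 2% to 5%: an assumption.
- Reactions are spread evenly over switchers and non-switchers: an assumption.

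Share of reactions lost = *s* × *m*:

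- 0.60 × 0.02 = 1.2%
- 0.60 × 0.05 = 3.0%

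Expected cases lost:

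- Hepatic: 19.0 × 0.012 = 0.23, and 19.0 × 0.030 = 0.57.
- Visual: 42.9 × 0.012 = 0.51, and 42.9 × 0.030 = 1.29.

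The plan also says 100 patients give at least a 95% chance of seeing a 3% reaction at least once. That reproduces: 1 − 0.97^100 = 95.2%. With 3.0% of reactions lost it becomes 1 − (1 − 0.03 × 0.97)^100 = 94.8%.

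If every child switched (*s* = 100%) and *m* = 5%, the loss would be 5%, or 0.95 of 19 hepatic cases.

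**The case against.** **The outcome is deduced.** The SAP nowhere says that a partly blank record counts as not related; this follows from combining SAP 7 with SAP 6.1. One could instead apply the item-level rule that SAP 7 gives for data with uncompleted cleaning: "The items will be handled as missing (category of categorical variable is" unknown). That does not make the event related either, and it leaves two programmers free to derive different outputs. The objection changes how the point is worded and leaves the gap open.

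**Such records should be uncommon.** Protocol 9.3 requires the investigator to assess and record causality, and Protocol 7.6.3.2 provides for sponsor queries. The case report form is not among the documents; it may offer a not-applicable option or prompt a query on a blank. This stands, and it is a reason to expect a small effect. SAP 7 does not rely on it, though: it sets a rule for blanks that remain.

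**Stronger readings the documents do not support:**

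- A reader might infer that every safety table is affected. SAP 8.2.3.2 tabulates adverse events regardless of causality, and the SAP 9 listings of adverse events and of events under the safety specifications keep them visible.
- A reader might infer that up to a fifth of hepatic cases could be lost, by taking 60 switchers with one event each, losing 60 × 5% = 3 events, and dividing by 13 or 19 hepatic cases (23% or 16%). That sets events of any type against hepatic cases alone. It also uses 13 as if it were an expected count, when it is the number reached with at least 95% probability. With 60% switching, losing a fifth would need 0.20 / 0.60 = 33% of switchers' events to show the pattern.
- A reader might take 6 of 7 uncounted patterns as a sign of scale. Pattern counts carry no frequency, and three of the six are also the ordinary record of a child on one form.
- A reader might conclude that any blank among the forms received should mean related. That would override an explicit 'not related' for the form in use because an earlier, stopped form was left blank, which conflicts with SAP 6.1.

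**Conclusion.** The point holds as a defect in a stated counting rule. In children who received more than one form, SAP 7 with SAP 6.1 lets a 'not related' mark for an earlier form cancel the plan's default to 'related', although causality for the form in use at onset is missing. Measured against that default, the error runs one way, towards fewer adverse drug reactions. Children on a single form are unaffected.

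The size is unknown and probably small. Under the assumed 60% switching and 2% to 5% of switchers' events, about 1.2% to 3.0% of reactions are lost: 0.2 to 0.6 of 19 expected hepatic cases and 0.5 to 1.3 of 42.9 expected visual events. The exact 95% interval for 19 of 100 runs from 11.8% to 28.1%, so the loss is well inside sampling error for common reactions. It could matter more for a reaction seen in one or two children, or for a small subgroup. The correction is justified because the rule contradicts the plan's own default and is cheap to repair, not because a large bias has been shown.

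**What to change.** Replace the causality sentence in SAP 7 with:

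> Causality is derived over the dosage forms the patient had received on or before the day of onset; forms not received by then are ignored. The event is counted as related if any of these forms is marked related, or if none is marked related and causality is missing for the form in use at onset (or, if treatment had ended or was suspended, the last form received).

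This keeps the protection for forms never taken. It also respects an explicit 'not related' for the form in use, whatever was left blank for an earlier one. Flag events counted as related through the missing rule in the adverse drug reaction listing, and report their number so that readers can see the effect.

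The cost is a small derivation from dosage form and treatment period, both already collected under Protocol 7.3.2, and possibly a slightly higher reaction count. If no such records exist, no result changes.

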8. STATISTICAL METHODS AND STATISTICAL ANALYSIS

8.1. Statistical Methods

8.1.1. Analysis of Continuous Data

Summary statistics (number of patients, mean, standard deviation, median, maximum, and minimum) will be calculated.

8.1.2. Analysis of Categorical Data

The frequency (number of patients) and proportion of each category will be calculated.

8.1.3. Analysis of Binary Data

The number of patients and proportion will be calculated. If the confidence interval of proportion is calculated, two-sided 95% confidence interval (exact method) will be calculated.

If the proportion is compared between subgroups, risk ratio and its 95% confidence interval, and risk difference and its 95% confidence interval will be calculated. In addition, risk ratio and its 95% confidence interval will be graphically presented (see Appendix 2). If the number of patients in each subgroup compared is ≤ 5 , the number of patients and proportion will be calculated but risk ratio and its 95% confidence interval, and risk difference and its 95% confidence interval will not be calculated.

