Version/ Date/ Author(s)	Summary of Changes/Comments
	
 - It was specified that risk ratio, etc. will not be calculated if the number of patients in each subgroup compared is ≤ 5 when the proportion is compared between subgroups based on risk ratio, etc. - Descriptions of test were deleted because no test will be performed in this investigation. 8.2.1. Overview of Patients 
 - Patients excluded from the analysis of effectiveness in the disposition of patients were divided into patients excluded from the analysis of clinical response and patients excluded from mycological analysis for clarification. - The number of patients for whom the case report form was not collected was deleted because these patients cannot be confirmed from the case report form data. - In the tabulation of listing of discontinuations and dropouts, it was clarified that discontinued patients have to be those observed for ≤ 16 weeks and a description on categories of timing was added. Tabulations of hepatic toxicity and visual events were moved to Section 8.2.3.1 Adverse Drug Reactions/Major Investigation Items. 8.2.2. Patient Background and Treatment History of Vfend 
 - The presence or absence of past or present history of visual disturbance was deleted because it can be confirmed by SOC based on the detailed results of tabulation of concurrent illness and past medical history. In addition, the presence or absence of past or present history of hepatic dysfunction was deleted because it can be confirmed based on data on the presence or absence of hepatic dysfunction. - Tabulations of diagnostic name and diagnostic name [definitive diagnosis] were added. 
 • Status of treatment of Vfend - The tabulation of dose per body weight was added to the status of treatment of Vfend because the target patients are children. In addition, it was additionally specified that the dose will be tabulated separately for patients aged < 12 years and ≥ 12 years whose body weight is less than 50 kg and those aged ≥ 12 years whose body weight is 50 kg or more. - Tabulations of the number of doses, dosage form on the first day, and changes, etc. in dosage form were deleted. 8.2.3. Safety Analysis 
 - The period of tabulation and analysis of adverse events and adverse drug reactions was provided. - The tabulation by known/unknown was added to tabulations of serious adverse drug reactions. - The section of safety specifications was deleted because it overlaps with 6.1 Safety Endpoints/Safety Specifications, and tabulations by intervention (change in Vfend treatment) and outcome were added. - The section of major investigation items was deleted because it overlaps with 6.1 Safety Endpoints/Major Investigation Items, and tabulations by intervention (change in Vfend treatment) and outcome were added. - The logistic regression analysis of major investigation items was deleted because of the

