5.4. Subgroups

Subgroup analyses of safety will be performed for the following patient background factors. Levels in parentheses are levels of subgroups, and underlined levels are the reference for calculation of risk ratio and risk difference.

- Hepatic dysfunction [absent, present]
- Renal dysfunction [absent, present]
- Age (children 1) [newborns (<1 month after birth), infants (≥ 1 month to <1 year), younger children (≥ 1 to <7 years), children (≥ 7 to <15 years)]
- Age (children 2) [<2 years, ≥ 2 years]
- Diagnostic name (name of infection) [invasive aspergillosis, pulmonary aspergilloma, chronic necrotic pulmonary aspergillosis, candidemia, esophageal candidiasis, candida peritonitis, bronchopulmonary candidiasis, cryptococcal meningitis, pulmonary cryptococcosis, fusariosis, scedosporiosis, other invasive fungal infections, others]
- Severity [mild, moderate, severe]
- Fever unresponsive to antibacterial agents [absent, present]
- Use of concomitant medications requiring precautions for coadministration [absent, present]
- Concomitant antifungal agents [absent, present]
- Prior medications (antifungal agents) [absent, present]
- Treatment period [<1 week, ≥ 1 to <2 weeks, ≥ 2 to <4 weeks, ≥ 4 to <8 weeks, ≥ 8 to <12 weeks, ≥ 12 to ≤ 16 weeks]
- Long-term treatment [≤ 12 weeks, >12 weeks]
- Dose on the first day (mg/kg) [<6, ≥ 6 to <7, ≥ 7 to <8, ≥ 8 to <9, ≥ 9 to <10, ≥ 10 , unknown]
- Mean maintenance dose (mg/kg) [<6, ≥ 6 to <7, ≥ 7 to <8, ≥ 8 to <9, ≥ 9 to <10, ≥ 10 , unknown]

Subgroup analyses of safety will be performed for the following:

- Pregnant and parturient women (pregnancy confirmed)
- Presence or absence of overdose^a

Patients who may meet contraindications in the package insert of Vfend (hereinafter referred to as contraindicated patients) will be extracted based on separately specified criteria, and subgroup analyses of safety will be performed.

Subgroup analyses of efficacy (clinical response) will be performed for the following patient background factors. Levels in parentheses are levels of subgroups, and underlined levels are the reference for calculation of risk ratio and risk difference.

- Hepatic dysfunction [absent, present]
- Renal dysfunction [absent, present]
- Age (children 1) [newborns (<1 month after birth), infants (≥ 1 month to <1 year), younger children (≥ 1 to <7 years), children (≥ 7 to <15 years)]
- Age (children 2) [<2 years, ≥ 2 years]

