8.2.3.5. Exploratory Analysis

The following exploratory analysis will be performed for factors affecting safety.

- The number and proportion of patients with adverse drug reactions will be tabulated by SOC and PT by factor with a risk ratio of ≥ 2 or ≤ 0.5 .

An additional analysis may be performed as necessary. The exploratory analysis will be reported only when results giving important interpretation are obtained.

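### The small-subgroup rule in SAP 8.1.3 asks that each compared subgroup have 5 or fewer patients, so read literally it does not suppress risk ratios for a tiny level set against a large one

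*SAP*

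**What the plan says.** SAP 8.1.3 (Analysis of Binary Data) calls for an RR and a risk difference, each with a 95% CI, whenever a proportion is compared between subgroups. The RR and its CI are also graphed. The exception reads "If the number of patients in each subgroup compared is" 5 or fewer; in that case "the number of patients and proportion will be calculated but risk ratio and its 95% confidence interval, and risk difference" and its CI are not produced. The version 3.0 entry in the SAP's amendment table words the rule the same way: "risk ratio, etc. will not be calculated if the number of patients in each subgroup compared is ≤ 5". I found no other minimum in the SAP, whether an either-subgroup rule, a minimum event count or a minimum total.

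Three other sections depend on the rule:

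- **SAP 5.4** lists the factors. Eight safety background factors have two levels: hepatic dysfunction, renal dysfunction, age under 2 years or not, fever unresponsive to antibacterials, medications requiring precautions, concomitant antifungals, prior antifungals, and long-term treatment. Others have many levels, including 13 for diagnosis. Underlined levels are the reference.
- **SAP 8.2.3.4** applies 8.1.3 to any ADR and to serious ADRs for every factor in 5.4.
- **SAP 8.2.3.5** tabulates ADRs "by SOC and PT by factor with a risk ratio of" at least 2 or at most 0.5.

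The planned sample size is 100 (Protocol 7.5.1).

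**The concern.** A minimum-size rule exists to stop ratios resting on a handful of patients from being reported as if they were informative. The usual danger is a small level against a large one, such as 1 patient against 99. A rule that needs both sides to be small does not cover that case.

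Factors that affect safety are a stated objective (Protocol 6, SAP 2.2). The same version 3.0 update dropped several analyses because too few patients would accrue, so sparse cells were a recognised problem. If the rule is programmed as written, RRs on levels of 1 to 5 patients enter the tables and the graph and can decide which factors get a further breakdown by SOC and PT.

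**Working it through.** **1. When can the rule fire?** Let the two compared levels have n1 and n2 patients. As written, suppression needs n1 ≤ 5 and n2 ≤ 5, hence n1 + n2 ≤ 10. For a two-level factor in 100 patients there are 101 possible splits (k against 100 − k, k = 0 to 100).

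- Each subgroup ≤ 5: 0 of 101 splits. The count is still 0 at totals of 50, 20 and 11; the first qualifying split is 5 against 5 at a total of 10.
- Either subgroup ≤ 5: k = 0 to 5 or 95 to 100, which is 12 of 101 splits.

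For a multi-level factor, each level is compared with the reference. As written, suppression needs the reference level to be ≤ 5 as well.

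**2. What would the interval show?** The SAP names no CI method for the RR. I assume log-Wald: RR × exp(±1.96 × SE), with SE² = 1/a − 1/n1 + 1/b − 1/n2 for a/n1 against b/n2. This reproduces the SAP's own Appendix 2 row for diagnosis: 3/221 against 18/3098 gives RR 2.34 (0.69 to 7.87), as printed.

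Now take one patient with an ADR against 19/99. The 19% is the hepatic toxicity rate quoted in the sample-size rationale and serves only as an illustration.

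- RR = (1/1)/(19/99) = 5.21.
- SE² = (1 − 1) + (1/19 − 1/99) = 0 + 0.0425, so SE = 0.206.
- 95% CI: 3.48 to 7.81.

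The one-patient level contributes zero variance, so the interval is falsely narrow. This happens whenever every patient in the small level has the event, since then a = n1.

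**3. How often would the 8.2.3.5 screen flag a tiny level by chance?** The documents give no overall ADR rate, so 10% and 40% are assumptions. I set n1 against 100 − n1 with the same true risk p in both, and summed exactly over a ~ Bin(n1, p) and b ~ Bin(100 − n1, p) with b > 0, counting RR ≥ 2 or ≤ 0.5.

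The answer depends on zero-event levels. The Appendix 2 example row 0/80 against 18/2056 shows a dash for the RR. If that convention is followed, such a level has no RR to screen. If RR = 0 is counted as ≤ 0.5, it is flagged.

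| n1 | 40%, zero-event level shows no RR | 40%, RR = 0 flagged | 10%, zero-event level shows no RR | 10%, RR = 0 flagged |
|---|---|---|---|---|
| 1 | 0.39 | 0.99 | 0.10 | 1.00 |
| 2 | 0.16 | 0.52 | 0.19 | 1.00 |
| 3 | 0.09 | 0.31 | 0.27 | 1.00 |
| 4 | 0.09 | 0.22 | 0.30 | 0.95 |
| 5 | 0.20 | 0.27 | 0.25 | 0.84 |

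**4. How much of this noise is due to the rule?** With zero-event levels left out, levels of 6, 8 and 10 patients, which an either-subgroup rule still admits, are flagged with probability 0.21, 0.19 and 0.20 at 10% risk. At 40% risk, a level of 6 gives 0.21, about the same as a level of 5. Even a 50 against 50 split gives 0.33 at 10% risk, though only 0.01 at 40%. Much of the noise therefore comes from screening on a point estimate in 100 patients.

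The model in steps 3 and 4 sets a level against everyone else, which fits two-level factors. For diagnosis, age bands or dose bands the comparator is the reference level alone. The underlining that marks it was not visible in the text I had, so I have not sized those comparisons.

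**The case against.** **The word may be loose translation.** The sentence can be taken as a check on each level separately, and the literal reading makes the rule inert for two-level factors, which the authors can hardly have wanted. This is plausible. But nothing else in the SAP settles it, and two programmers could produce different tables. A reader might go further and infer that RRs on tiny levels were in fact printed. The documents do not show how the rule was implemented.

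**The rule is not wholly dead.** A reader might infer that it can never fire. That goes too far: SAP 3 plans periodic interim analyses, and one with 10 or fewer patients could meet the condition. So could a multi-level factor whose reference level is tiny.

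**Chance flags are not near-certain.** A reader could take the values near 1.00 in the table as the size of the problem. They arise only if RR = 0 is treated as ≤ 0.5, and the Appendix 2 example points the other way. That appendix gives examples and is not a stated rule, so both sets of figures are shown.

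**Little rides on these RRs.** SAP 4.1 calls the study non-confirmatory, and SAP 4.2 has no decision rules. A flag leads only to a further descriptive tabulation, and exploratory results are reported only if they add important interpretation. Counts and proportions are shown, so a reader would see 1/1 beside the ratio. All of this stands. It lowers the severity, but the rule as worded still misses the case it appears to be meant for.

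**Conclusion.** The point holds as a wording error of modest consequence. Read literally, the rule cannot suppress anything for a two-level factor whose levels total more than 10 patients, which includes the planned 100. For multi-level factors it works only when the reference level is also 5 or fewer. RRs on levels of 1 to 5 patients would be reported and plotted, sometimes with intervals far too narrow, and could enter the exploratory screen.

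The first conclusion is exact and needs no assumed rates. The interval example assumes the log-Wald method. The flag probabilities rest on assumed ADR risks, equal risk in both groups and the handling of zero-event levels, and should be read as illustration. The documents do not support a claim that a safety conclusion is compromised.

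**What to change.** Replace the condition in SAP 8.1.3 with: *If either of the two subgroups compared has 5 or fewer patients, give the number and proportion only; do not calculate the RR, the risk difference or their CIs.* For multi-level factors this applies to each level-against-reference pair.

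The cost is a small edit to one sentence of the SAP. A few RRs on very small levels disappear from the tables, the graph and the 8.2.3.5 screen, while the counts and proportions remain. The edit does not cure the noise of that screen for levels just above 5, so flagged factors should still be read with their counts alongside.
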